2.3.5 Special statistical consideration

ASRS score calculation

Due to differential scale scoring between ASRS (2-5 years) and ASRS (6-18 years), the total score is unlikely to be weighed and used as a single composite endpoint. Instead, the standardized T score of ASRS in total, and two subscales (Social/Communication, SC and Unusual Behaviors, UB) will be calculated and combined between ASRS (2-5 years) and ASRS (6-18 years). The formulas and items for T score calculation is provided in Appendix Table 2.

2.3.6 Statistical software

STATA® (version 15.1, Stata Corp, Texas, USA) will perform all data analyses and generate most data displays. R4.1.2 (Vienna, Austria) may also be used for some data analyses and generating statistical graphs.

3. Change log

Version	Date	Reasons for change
0.0	18 Aug 2023	Clinical Trial registration
1.0	7 Mar 2024	Clinical assessments at M1 and M2 were cancelled because clinicians found it difficult for subjects to keep intense clinical visits;
2.0	10 Jan 2025	Secondary endpoints updated
2.5	17 Feb 2025	Supportive endpoint analysis and Other sensitivity analysis updated.
3.0	28 Feb 2025	As drop-outs in M6,M9,M12 for Gesell, CARS and WISC are more than expected (<10 at each visit), ANCOVA will be preferred as an alternative.

4. Appendix

Table 1 The formulas for calculating Cohen's D values

Condition	Statistical display	Formula
-----------	---------------------	---------

Population estimated mean group difference in change over time	$\beta_{T-T0} (95\%CI)$	$\frac{\beta_{T-T0}}{(upperlimit - lowerlimit) \times \frac{2 \times 1.96}{\sqrt{N_{T-T0}}}}$
--	-------------------------	---

Abbreviations: A:placebo group; B, taurine group; T, time visit; T0,baseline.

Table 2 The formulas for calculating ASRS T-score

Condition	Age range	Raw score of items	Formula ¹
SC	2-5 years	$\Sigma (i1 i3 i4 i5 i7 i13 i14 i15 i16 i17 i18 i19 i21 i22 i24 i25 i28 i29 i30 i32 i33 i35 i36 i37 i38 i40 i43 i44 i49 i50 i51 i52 i54 i55 i57 i61 i62 i63 i67)$	$50+10 \times ((\text{raw score} - 50.06)/10.12)$
	6-18 years	$\Sigma (i3 i4 i8 i9 i12 i23 i28 i31 i32 i33 i39 i42 i43 i45 i55 i56 i61 i69 i7)$	$50+10 \times ((\text{raw score} - 24.3)/11.95)$
UB	2-5 years	$\Sigma (i2 i8 i9 i10 i11 i12 i20 i26 i27 i39 i41 i42 i45 i46 i47 i48 i53 i56 i60 i64 i65 i69 i70)$	$50+10 \times ((\text{raw score} - 50)/10.51)$
	6-18 years	$\Sigma (i2 i13 i17 i20 i21 i22 i24 i25 i26 i27 i29 i38 i40 i46 i48 i49 i50 i51 i54 i62 i63 i65 i67 i68)$	$50+10 \times ((\text{raw score} - 27.74)/10.79)$
Total	2-5 years	-	$50+10 * ((T \text{ score}_{SC+UB} - 50.03)/10.35)$
	6-18 years	-	$50+10 * ((T \text{ score}_{SC+UB} - 47.89)/7.85)$

¹the reference values for calculation are based on Chinese reference population^{3,4}.

Abbreviations: SC, Social/Communication; UB, Unusual Behaviors

5. References

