2.3 Statistical analysis

Effect endpoints will be analyzed using the FAS and PPAS; safety endpoints will be analyzed using the SAS.

Results from effect endpoints will generally be accompanied by two-sided 95% confidence intervals(CI) and corresponding p-values. Significant difference will be claimed if two-sided 95% CI lie away from null. Effect size will be evaluated by corresponding Cohen's D values, which are calculated as mean difference between groups divided by standard deviation for each endpoint in corresponding analysis set (details in appendix Table 1).

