2.3.2 Primary endpoints

The primary endpoints are defined as change in scores of ASD-related scales from baseline at M0 to M3.

Descriptive statistics of primary endpoints

Mean and standard deviation of primary endpoints at each visit, and changes of mean and standard deviation from baseline to each visit will be presented.

Primary analysis for primary endpoints

Using unimputed data of primary endpoints in FAS, exploratory mixed-effects models, preferably generalized linear mixed model (GLMM) for repeated measures analysis, in the condition for endpoints of >2 visits. This analysis investigates if there are group-specific differences over time. The maximum likelihood method will be used to estimate the mean difference between the two groups and their 95% CI, with Gaussian distribution and identity link function; baseline score, group (group), time point (visit) and group \times visit interaction as fixed effects. The time point(visit) is treated as categorical variable in the models. Random slope with unstructured covariance will be preferred as priority; if convergence is not able to be achieved, random intercept will be performed as an alternative.

Otherwise, ANCOVA will be performed to estimate the mean difference between the two groups and their 95% CI, with group (group) as independent variable, and baseline score, time point (visit) and group \times visit interaction as covariates for outcomes with only 2 visits available. The available visits are defined as >10 observations at a single visit. The reason for this alternative method is explained in the Change Log.

For imputed data of primary endpoints, multiple imputation will be considered for handling missing outcomes. More details are described in 2.3.4.

Secondary analysis for primary endpoints

● Per-protocol analysis

Using unimputed data of primary endpoints in PPAS, exploratory mixed-effects models, preferably generalized linear mixed model (GLMM) for repeated measures analysis, in the condition for endpoints of >2 visits. Otherwise, ANCOVA will be performed if only 2 visits are available for the scores of ASD-related scales. The statistical method is the same as primary analysis for primary endpoints.

● Covariate-adjusted analysis

Covariate-adjusted analysis for primary endpoints is performed in FAS and PPAS using the same statistical method as primary analysis.

Covariates are baseline values (missing imputed) including:

- Age (years)
- Sex (1,Boy;2,Girl)

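### The Cohen's D formula in Appendix Table 1 does not divide by the standard deviation that section 2.3 names, and as printed its result grows with sample size

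*SAP*

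**What the plan says.** Section 2.3 says that effect size will be judged by Cohen's D, "calculated as mean difference between groups divided by standard deviation for each endpoint in corresponding analysis set", and refers to Appendix Table 1 for details.

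Table 1 has one row, labelled "Population estimated mean group difference in change over time". Its numerator is the model estimate β. Its denominator is printed as "upperlimit - lowerlimit) \times \frac{2 \times 1.96}{\sqrt{N_{T-T0": the width of the confidence interval, multiplied by 2 × 1.96 and divided by the square root of N.

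The line under the table reads "Abbreviations: A:placebo group; B, taurine group; T, time visit; T0,baseline". It does not define N, and A and B do not appear in the formula as shown.

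Section 2.3.2 sets what is standardised and where the interval comes from. On the endpoint: "The primary endpoints are defined as change in scores of ASD-related scales from baseline at M0 to M3". The model is fitted "with Gaussian distribution and identity link function; baseline score, group (group), time point (visit", with a group-by-visit term, so baseline score is adjusted for. On which visits count: "The available visits are defined as >10 observations at a single visit".

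**The concern.** The text and the table describe different quantities. The text asks for a standard deviation. The table contains the parts of a back-calculation of an SD from a confidence interval, but the constant 3.92 and √N are on the wrong sides of the fraction. If so, D depends on how many children contribute as well as on the effect.

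That matters because N will differ between scales, visits and analysis sets (FAS and PPAS). The change log already reports fewer than 10 at each of M6, M9 and M12 for Gesell, CARS and WISC. The trial is exploratory and has no sample size calculation (sections 1.1.4 and 2.1), so readers are likely to lean on D to judge magnitude. The same true effect could look large on one scale and small on another through N alone, and the values could not be held against the usual D benchmarks.

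**Working it through.** The SAP reports no numerical D or SD, so there is no figure to reproduce. The check is on the formula itself.

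**Inputs.** Two-sided 95% CI (section 2.3); 60 children, 30 per group (section 2.1); more than 10 observations for an available visit (section 2.3.2); denominator from Table 1. Assumed: equal arms, common SD, no covariate adjustment. The SD cancels, so set SD = 1.

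**Formula as printed.** Let n = N/2 per arm.

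- SE = SD × √(2/n) = 2 × SD/√N
- CI width W = 3.92 × SE
- Printed denominator = W × 3.92/√N = 3.92² × SE/√N = 15.37 × SE/√N
- With N the total: 2 × 15.37 × SD/N = 30.73 × SD/N, so printed D = true D × N/30.73
- With n per arm under the root: √2 × 15.37 × SD/n = 21.73 × SD/n, so printed D = true D × n/21.73

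| Reading of N | Value | Denominator (SD = 1) | Printed D / true D |
|---|---|---|---|
| Total | 60 | 0.512 | 1.95 |
| Total | 40 | 0.768 | 1.30 |
| Total | 31 | 0.991 | 1.01 |
| Total | 20 | 1.537 | 0.65 |
| Total | 11 | 2.794 | 0.36 |
| Per arm | 30 | 0.724 | 1.38 |
| Per arm | 20 | 1.087 | 0.92 |
| Per arm | 10 | 2.173 | 0.46 |

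Eleven children cannot split equally. With 5 and 6, SE = √(1/5 + 1/6) = 0.606, the denominator is 0.606 × 15.37/√11 = 2.81, and the ratio is still 0.36.

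With N the total, a true D of 0.50 is thus reported as 0.98 at 60 children and 0.33 at 20. The denominator equals the SD only by coincidence, at about 31 children in total, or at about 21.7 per arm (about 43 in total) if N is per arm. For the same data, the two readings of N give D values that differ by a factor of √2.

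**Operator read as a division.** The denominator becomes W × √N/3.92 = SE × √N. That is 2.00 × SD with N total, or 1.41 × SD with n per arm, at every sample size. D is then ×0.50 or ×0.71.

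**A back-calculation that works.** (W/3.92)/√(1/nA + 1/nB) equals the SD here, and returned 0.50 for a true D of 0.50 at every total from 20 to 240.

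**With baseline adjustment.** The interval then carries a residual SD. Relative to the SD of change it is √((1 + r)/2), where r is the baseline–outcome correlation: 0.866 at r = 0.5 and 0.922 at r = 0.7. ANCOVA of change on group and baseline was simulated with 4,000 runs per cell, t-based intervals, N total and true D 0.50 against the SD of change. The correlations are assumed, and the ranges below cover r = 0.5 and 0.7. Median D:

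| Total N | Printed formula | Observed pooled SD | CI back-calculation, t quantile |
|---|---|---|---|
| 20 | 0.32–0.34 | 0.50–0.51 | 0.53–0.56 |
| 40 | 0.69–0.71 | 0.50–0.52 | 0.55–0.57 |
| 60 | 1.04–1.09 | 0.50–0.51 | 0.54–0.57 |

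**The case against.** The strongest objection is that the dependence on N rests on one symbol in a nested fraction read from a PDF by a program. If the authors wrote a division, the formula is the familiar single-group back-calculation, D is off by a constant, and comparability across N is not lost for the reason given. A and B are defined but not used in the visible formula, so part of the table, perhaps including a definition of N, may not have come through. This stands as a caveat: the growth with N holds for the formula as printed. It does not rescue the formula, because neither operator, with N read either way, returns the SD. A misread is also not shown; a division sign elsewhere in the SAP (section 2.3.1) came through correctly.

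Second, D drives no decision. Significance is claimed from the interval and the trial is exploratory. That is true, and it limits the harm to a reported descriptive measure.

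Third, section 2.3 does not say that the SD must be observed, pooled or unadjusted. A model-based SD is a legitimate choice if labelled as one. This also stands; the residual-SD point is about labelling and is secondary.

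Fourth, the simulation used change on group and baseline, whereas section 2.3.2 lists visit and group-by-visit terms as well. With stacked two-visit data and those terms, printed D at 60 children was about 1.00–1.04 instead of 1.04–1.09, so the conclusion is unchanged.

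**Conclusion.** The formula is wrong as written. Table 1 does not compute what section 2.3 defines, under either reading of the operator or of N. As printed, D is inflated 1.95-fold at the planned 60 children if N is the total, or 1.38-fold if N is per arm, and it is deflated at small visits (×0.65 at 20 in total, ×0.36 at 11). Near 31 in total, or about 22 per arm, the error is small. Read as a division, D is understated by 50% or 29% at every N.

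These multipliers assume an unadjusted comparison with equal arms. Baseline adjustment shifts them modestly, under assumed correlations of 0.5 to 0.7, and does not remove the dependence on N. β, its confidence interval and the p-value are unaffected.

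**What to change.** Replace the Table 1 denominator with the observed pooled between-subject SD of the change from baseline, at the visit and in the analysis set concerned. Section 2.3 should say so explicitly, since it now names only a standard deviation. As a check, β = 0.5 with a pooled SD of 1 must return 0.50.

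If a back-calculation from the interval is kept, use [(upper − lower)/(2 × the quantile actually used)]/√(1/nA + 1/nB), with nA and nB the children contributing at that visit. Label the result as standardised by the model-based, baseline-adjusted SD. Restrict it to the one-row-per-child ANCOVA: a mixed-model interval borrows information across visits, and counts at a single visit do not then recover an SD exactly.

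Define every symbol under the table, and check the printed operator against the analysis code.

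The cost is one line in the appendix and one line of code. If the code follows the printed formula, reported D falls where N is well above the crossover (about 31 in total if N is the total, about 43 in total if N is per arm) and rises where it is well below. No estimate, interval or p-value changes.
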